4.2.6. Patient Health Questionnaire (PHQ-9)

The PHQ-9 is used as a subject-reported measure of depressive symptomatology. The PHQ-9 is a 9-item scale, where each item is rated on a 4-point scale (0=Not at all, 1=Several Days, 2=More than half the days, and 3=Nearly every day), with a total score range of 0 to 27. The recall period is 2 weeks.

Descriptive statistics (N, mean, median and range) of total score and as well changes from baseline will be provided by treatment group.

In addition, analyses on changes from baseline in PHQ-9 total score may also be conducted using the similar aforementioned MMRM for the primary analyses.

4.2.7. Snaith–Hamilton Pleasure Scale (SHAPS)

Anhedonia, the inability to experience pleasure, is a core symptom of depression. The Snaith–Hamilton Pleasure Scale (SHAPS) is a short, 14-item instrument to measure anhedonia, which has been shown to be valid and reliable in normal and clinical samples. Each of the 14 items has a set of four response categories: Definitely Agree, Agree, Disagree, and Definitely Disagree.

There will be two definitions for total score. The (protocol) definition 1: Definitely Agree (=1), Agree (=2), Disagree (=3), and Definitely Disagree (=4). The definition 2: Definitely Agree (=0), Agree (=0), Disagree (=1), and Definitely Disagree (=1). A SHAPS total score will be calculated as the sum of the 14 item scores. A higher total score indicates higher levels of state anhedonia.

Descriptive statistics (N, mean, median and range) of total score (for both definitions) and as well changes from baseline will be provided by treatment group.

4.2.8. Functional Assessment of Chronic Illness Therapy-Fatigue (FACIT Fatigue)

The FACIT-Fatigue is a questionnaire that assesses self-reported tiredness, weakness, and difficulty conducting usual activities due to fatigue. The subscale consists 13-item instrument to measure fatigue. Each of the 13 items has a set of five response categories: Not at all (=0), A little bit (=1), Somewhat (=2), Quite a bit (=3) and Very much (=4). A total FACIT-Fatigue subscale score will be calculated as the sum of the 13 item scores (reserved scores [4 – score] for all except for 2 items: "I have energy" and "I am able to do my usual activities"), and ranges from 0 to 52, with a higher score indicating less fatigue.

Descriptive statistics (N, mean, median and range) of total score and as well changes from baseline will be provided by treatment group.

4.3. Exploratory Efficacy Endpoint

4.3.1. Inventory of Depressive Symptomatology – Clinician Rated 30 (IDS-C30)

The clinician-rated IDS is a 30-item, depression-specific symptom severity rating scale. The IDS is designed to measure the specific signs and symptoms of depression, including melancholic, atypical and anxious features. Scores range from 0 to 84 with higher scores representing greater severity of depressive symptoms. Only one of items 11 or 12 and of items 13 or 14 need to be rated. If both item 11 and 12 (or 13 and 14) are completed by accident, the highest of the two item scores will be used for calculating the total score.

Change from baseline in IDS-C30 score will be calculated. Descriptive statistics (N, mean, median and range) of the numerical scores and as well changes from baseline will be provided by treatment group.

In addition, analyses on changes from baseline in IDS-C30 total score may also be conducted using the similar aforementioned MMRM for the primary analyses.

4.3.2. Childhood Trauma Questionnaire (CTQ)

The self-report includes a 28-item test that measures 5 types of maltreatment – emotional, physical, and sexual abuse, and emotional and physical neglect. A 5-point Likert scale is used for the responses which range from Never True to Very Often True. A total CTQ score will be calculated as the sum of the 28 item scores (reserved scores for items 2, 5, 7, 10, 13, 16, 19, 22, 26 and 28), and ranges from 28 to 140, with a higher score indicating a more server childhood trauma.

Physical abuse is 'yes' if sum of CTQ items 9, 11, 12, 15, 17 is 8 or larger. Physical neglect is 'yes' if sum of CTQ items 1, 2 (R) (where R stands for reserving score), 4, 6, 26 (R) is 8 or larger. Sexual abuse is 'yes' if sum of CTQ items 20, 21, 23, 24, 27 is 8 or larger. Emotional abuse is 'yes' if sum of CTQ items 3, 8, 14, 18, 25 is 10 or larger. Emotional neglect is 'yes' if sum of CTQ items 5 (R), 7 (R), 13 (R), 19 (R), 28 (R) is 15 or larger.

Descriptive statistics (N, mean, standard deviation, median and range) of the numerical total scores may be provided by treatment. A frequency distribution of CTQ will be provided by treatment group. Frequency distributions of physical abuse, physical neglect, sexual abuse, emotional abuse and emotional neglect will also be provided by treatment group.

4.3.3. MINI International Neuropsychiatric Inventory (MINI)

The Mini-International Neuropsychiatric Interview (M.I.N.I.) is a short structured diagnostic interview for psychiatric disorders.

Frequency distributions of diagnostic psychiatric disorders will be provided by treatment group.

5. BIOMARKERS

5.1. Biomarker Variables

Biomarkers consist of hsCRP, ACTH, Adiponectin, serum BDNF, IGF1, IL6R, Leptin, IL-6, IL-1b, IL-10, TNFa, saliva Cortisol, serum Cortisol, Kynurenine pathway metabolites, and a total of 92 SNPs related to above HPA, metabolic, and inflammatory biomarkers.

5.2. Analysis Methods

5.2.1. hsCRP as a predictor of response

HDRS17 changes and percent changes from screening on week 12 (Δ_{w12}^{HDRS17}) will be modeled as a function of screening hsCRP including BMI, sex, and age as covariates for subjects treated with sirukumab. hsCRP is determined to have significant predictive power if it models a significant amount of variance in Δ_{w12}^{HDRS17} from screening at p <= 0.1 Scatter plots of Δ_{w12}^{HDRS17} versus hsCRP will be created and annotated with regression modeling results including regression coefficients for model variables and corresponding significance levels and coefficients of determination R² and R²_{partial} and R²_{reduced} for the reduced model. The reduced model is the full model with the variable of interest (hsCRP) omitted.

Logistic models will be used to gauge the potential of screening hsCRP as a predictor of remitters (week 12 HDRS17 <= 7) and responders with (50% improvement in HDRS17 on week 12). In both models, covariates will include BMI, sex, and age. Screening HDRS17 levels will also be used as a covariate in the model predicting remission. ROC curves will be generated for each model in addition to AUC and model accuracies.

To demonstrate specificity of hsCRP predictive power, modeling is also carried out on placebo treated subjects and the outcomes are compared to those for subjects treated with sirukumab.

In order to enable comparison of hsCRP performance with that of other biomarkers which were measured at baseline, the above models will be repeated substituting screening visit with baseline.

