1.4. Sample Size Justification

Approximately 192 subjects will be enrolled in this study, with approximately 96 subjects randomized per treatment group.

The target study population is male and female subjects with MDD who have had a suboptimal response to standard oral antidepressant therapy; have failed no more than 3 antidepressant treatments in the current major depressive episode; approximately 142 subjects with screening hsCRP $\geq 0.300 \text{ mg/dL}$ (SI 3.00 mg/L) and approximately 50 subjects with screening hsCRP<0.300 mg/dL (SI 3.00 mg/L) will be enrolled.

The expected final sample size of 142 for subjects with screening hsCRP ≥ 0.300 mg/dL (SI 3.00 mg/L) was determined based on the assumption of an effect size of at least 0.5 for the HDRS17 (mean change from baseline to week 12 endpoint between the sirukumab and placebo groups of 4 with SD=8). This is considered to be a clinically relevant difference in a population with suboptimal response to standard oral antidepressant therapy. Power is set at 90.0%, with a 1-sided alpha of 0.125 and a 12-week drop-out rate of 25%. It was also assumed that 10% of the randomized subjects would be excluded from the primary efficacy analysis due to having hsCRP ≥ 3.00 mg/L at screening but not at baseline.

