5.2.2. Alternate predictors of response

5.2.2.1 Tier A biomarker panel

The Tier A biomarkers panel consists of inflammation-related analytes: IL-6, IL6R, IL-10, IL-1b, and TNFa. Kynurenine pathway metabolites kynurenine, tryptophan, 3-OH kynurenine, kynurenic acid, and quinolinic acid are also included in Tier A as this pathway has been shown to drive inflammatory processes.

 Δ_{w12}^{HDRS17} will be modeled as a function of each analyte in the high-priority panel measured at baseline with BMI, sex, and age as covariates. Analyte levels that model a significant amount of variance (p ≤ 0.1) in Δ_{w12}^{HDRS17} will be compared against performance of the baseline hsCRP model from Section 5.2.1 Model performance will be compared using Akaike Information Criterion (AIC) or non-parametric equivalent. Bonferroni Family Wise Error Rates (FWER) will be reported in addition to uncorrected p values. Models with FWER ≤ 0.1 and better performance than the hsCRP model are identified as alternate candidate predictive biomarkers.

Logistic models for identified alternate candidate biomarkers, if any, will be generated for predicting remission and response and the results will be compared to the corresponding outcome of logistic models for baseline hsCRP in Section 5.2.1.

Multivariate models using supervised machine learning will also be used to predict Δ_{w12}^{HDRS17} , response, and remission using hsCRP and Tier A analytes. 80% of the samples will be used for training with 20% set aside for model testing. ROC curves will be generated for each of model in addition to AUC and model accuracies.

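### SAP 5.2.1: the logistic models are judged by whole-model AUC and accuracy, which do not isolate what hsCRP adds

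*SAP*

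**What the plan says.** SAP 5.2.1 states the purpose: "Logistic models will be used to gauge the potential of screening hsCRP as a predictor of remitters", and likewise of responders. Both logistic models adjust for BMI, sex and age; the remission model also adjusts for screening HDRS17. The stated output is: "ROC curves will be generated for each model in addition to AUC and model accuracies".

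For the linear model of HDRS17 change, the same section asks for regression coefficients with significance levels, a partial R² and the R² of a reduced model, defined thus: "The reduced model is the full model with the variable of interest (hsCRP) omitted". It also sets a rule for hsCRP at p ≤ 0.1. Neither the reduced model nor the rule is carried over to the logistic models. The models are refitted in placebo subjects to show specificity, with no criterion for the comparison.

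SAP 5.2.2.1 reuses the logistic models. For any candidate marker found there, "the results will be compared to the corresponding outcome of logistic models for baseline hsCRP in Section 5.2.1". Sections 5.2.2.1 and 5.2.2.2 set aside 20% of samples to test the machine-learning models. Section 5.2.1 names no split or resampling.

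**The concern.** An AUC or accuracy for a model with four or five predictors measures all of them together. It can be well above 0.5 because a covariate is prognostic, or because the coefficients were tuned to the subjects on whom the model is scored, while hsCRP contributes nothing. The remission model is most exposed, since remission is a threshold on HDRS17 and screening HDRS17 is among the predictors.

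Accuracy has a further problem. When the event is uncommon, predicting that nobody has it is already accurate, so a high figure says little.

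At stake is how the exploratory biomarker results are read. A reader shown an ROC curve with an AUC of 0.65 to 0.70 under the title of hsCRP as a predictor may credit hsCRP with it.

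**Working it through.** **1. Reproducing the plan's figure, and the number of subjects.** The SAP states no AUC. Its computed design figure is 142 subjects with screening hsCRP ≥ 3.00 mg/L (SAP 1.4). The inputs are a difference of 4, SD 8, one-sided alpha 0.125, power 90%, dropout 25% and a further 10% excluded.

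- n per arm = 2(z₀.₈₇₅ + z₀.₉₀)² × SD²/difference² = 2(1.150 + 1.282)² × 64/16 = 47.3, so 48; total 96.
- 96 / 0.75 / 0.90 = 142.2, against 142 stated. It reproduces.

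For the models in 5.2.1, SAP 1.4 gives: "Approximately 192 subjects will be enrolled in this study, with approximately 96 subjects randomized per treatment group". The sirukumab arm therefore has at most about 96 subjects, and 96 × 0.75 = 72 with a Week 12 score. At 20% remission that is 72 × 0.20 ≈ 14 remitters for a five-predictor model.

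**2. Simulation with every predictor useless.** There were 1,500 simulated data sets per setting, with independent covariates and a logistic model fitted and scored on the same subjects. The response model holds hsCRP, BMI, sex and age; the remission model adds HDRS17. The SAP gives no event rates, so these are assumed. The true AUC is 0.50. Differences are averaged before rounding. The no-information rate is the accuracy of always predicting the commoner outcome.

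| n | Outcome, rate | Mean AUC, full (5th–95th percentile) | Mean AUC without hsCRP | Difference | Accuracy | No-information rate |
|---|---|---|---|---|---|---|
| 72 | Response 30% | 0.639 (0.556–0.731) | 0.619 | 0.021 | 0.708 | 0.699 |
| 72 | Response 40% | 0.630 (0.556–0.716) | 0.612 | 0.019 | 0.636 | 0.602 |
| 72 | Remission 20% | 0.683 (0.591–0.787) | 0.661 | 0.022 | 0.804 | 0.801 |
| 72 | Remission 30% | 0.660 (0.579–0.752) | 0.642 | 0.018 | 0.715 | 0.701 |
| 96 | Response 30% | 0.618 (0.548–0.699) | 0.599 | 0.018 | 0.704 | 0.699 |
| 96 | Response 40% | 0.611 (0.544–0.686) | 0.595 | 0.016 | 0.625 | 0.602 |
| 96 | Remission 20% | 0.653 (0.575–0.746) | 0.636 | 0.018 | 0.800 | 0.798 |
| 96 | Remission 30% | 0.636 (0.563–0.717) | 0.620 | 0.016 | 0.707 | 0.699 |

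Rarer remission makes it worse: at an assumed 15% the mean apparent AUC is 0.703 (n = 72) or 0.675 (n = 96).

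**3. Screening HDRS17 prognostic, hsCRP useless.** With an assumed odds ratio of 2 per SD, the mean remission AUC is about 0.72 to 0.74 over n = 72 to 96. With a weaker effect (log odds 0.5 per SD, odds ratio e^0.5 = 1.65) and 20% remission it is 0.720 (n = 72) or 0.698 (n = 96), against 0.704 and 0.684 without hsCRP. Here hsCRP accounts for 0.016 and 0.014.

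**4. Does the repair work?** Bootstrap optimism correction brought the all-null AUCs down to 0.54 to 0.56. The comparison of full with reduced model shows the small share due to hsCRP directly, as the table does.

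**The case against.** The strongest reply is that nothing is decided on these AUCs, and that is right. The SAP calls hsCRP predictive on the linear model at p ≤ 0.1, with partial and reduced R². Candidate markers are chosen on linear-model p ≤ 0.1, family-wise error ≤ 0.1 and a better AIC than hsCRP. Logistic models follow only for markers already chosen, and no AUC threshold is set. A reader might infer that the AUCs are the trial's test of hsCRP, or that they tilt the choice of alternate markers. The SAP supports neither.

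Second, when a candidate's logistic model is set beside the hsCRP one with the same covariates, both carry similar inflation, so it largely cancels. This also stands: no systematic advantage to hsCRP has been shown. What remains is noise. Swapping one useless marker for another changed the apparent AUC with an SD of about 0.03 to 0.04, and the SAP gives no criterion for the comparison.

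Third, the placebo refit would show similarly inflated AUCs if hsCRP were useless. That is real context. It does not isolate hsCRP within an arm, since AUCs can differ between arms through covariates or chance.

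Fourth, in-sample scoring is inferred from silence, and any logistic fit yields a coefficient and test for hsCRP. Both are fair. But the SAP lists coefficients and significance levels for the linear model and not for these, and even a hold-out AUC would still mix in the covariates. Finally, the failure to separate hsCRP from severity concerns the remission model only; the response model does not contain HDRS17.

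**Conclusion.** The point holds for the exploratory logistic models in SAP 5.2.1 and their reuse in 5.2.2.1. As written, the named outputs do not measure what the models are meant to gauge. A useless hsCRP would still come with a mean apparent AUC of about 0.61 to 0.68 if all predictors are null, or about 0.72 to 0.74 for remission if screening HDRS17 is prognostic. Only about 0.01 to 0.02 of that is due to hsCRP. Remission accuracy would be close to that of predicting that nobody remits.

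These sizes rest on 72 to 96 sirukumab subjects, assumed event rates of 20% to 40%, an assumed odds ratio of 2 per SD for HDRS17, independent covariates and in-sample scoring. The missing reduced-model comparison depends on none of these assumptions. The primary analysis and the formal biomarker rules are unaffected.

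**What to change.** In SAP 5.2.1, and for the logistic models in 5.2.2.1:

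- Extend the reduced-model comparison already used for the linear model. Report the likelihood-ratio test for the marker, and the AUC of the full and reduced models with their difference.
- Report AUCs corrected for optimism by an internal resampling method, either bootstrap or cross-validation.
- Show each accuracy beside the no-information rate.

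The cost is a few sentences in the SAP and a short resampling routine. No new data are needed. The reported AUCs will be lower than under the present wording.

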2.5.3. Biomarker Analysis Set

Biomarker analyses will be performed on biomarker analysis set. It will include all randomized subjects who receive at least 1 dose of study drug in the double-blind phase and have at least 1 sample obtained.

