4.2.2. Analysis Methods

The primary efficacy analyses will be conducted using mITT1 analysis set. The primary comparison will be between sirukumab and placebo using the primary efficacy endpoint, i.e., change in HDRS₁₇ total score from baseline to Week 12.

A mixed effects model using repeated measures (MMRM) with time, treatment, country, screening hsCRP stratification and time-by-treatment interaction as factors, baseline HDRS₁₇ total score as a continuous covariate, and a random subject effect, will be conducted. An unstructured variance-covariance matrix will be used (if there are convergence issues with the unstructured variance-covariance matrix, another suitable matrix structure will be chosen based on the LR test or the AIC). The contrast on Week 12 changes will be of primary interest, and tested at one-sided alpha level of 0.125. Descriptive statistics for values and changes from baseline will be provided for HDRS₁₇ including individual items and total score, at each time point of the double-blind treatment phase. Time profile of HDRS₁₇ total score for individual subjects will be represented graphically over time by treatment group.

Sensitivity analyses on the primary endpoint will also be conducted. Sensitivity analyses will be using the aforementioned MMRM using mITT3 and mITT2 analysis sets.

The primary endpoint with the aforementioned MMRM analyses may also be explored in subgroups such as 5 types of maltreatment based on CTQ (physical abuse, physical neglect, sexual abuse, emotional abuse and emotional neglect) and baseline BMI status (≤ 25 (normal) vs. >25 (abnormal) or ≤ 30 (normal) vs. >30 (abnormal)).

In addition, the primary endpoint using similar MMRM analyses with additional covariates such as CTQ total score or others may also be explored.

Secondary Efficacy Endpoints

Analyses of secondary efficacy endpoints will be mainly based on the mITT2 analysis set. Analyses on the secondary efficacy endpoints may also be conducted using the aforementioned MMRM using mITT1 and mITT3 analysis sets.

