4.2.4. Responders and Remitters

Subjects who have HDRS₁₇ score \leq 7are considered as remitters while those who have \geq 50% improvement in HDRS₁₇ total score from baseline at week 12 are considered responders. The response rate or remission rate at Week 12 in sirukumab will be compared with that in placebo using a logistic regression model including baseline HDRS₁₇ score, screening hsCRP stratification, country and treatment.

Response rate or remission rate at Week 12 will be provided by treatment group for the following subgroups:

(1) Screening hsCRP stratification;

(2) TRD status (TRD vs. non-TRD).

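### Section 5.2.1 calls hsCRP predictive from sirukumab subjects alone, and its placebo specificity step plans no estimate, interval or test of the between-arm difference in slopes

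*SAP*

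**What the plan says.** SAP section 5.2.1 models Week 12 change and percent change in HDRS17 on screening hsCRP, "including BMI, sex, and age as covariates for subjects treated with sirukumab". The decision rule belongs to that model: "hsCRP is determined to have significant predictive power if it models a significant amount of variance in" the Week 12 HDRS17 change, at p <= 0.1. The output includes "regression coefficients for model variables and corresponding significance levels", with full, partial and reduced-model R-squared.

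The section then sets a further aim: "To demonstrate specificity of hsCRP predictive power, modeling is also carried out on placebo treated subjects and the outcomes are compared" with the sirukumab results. That sentence is the whole method for specificity. The models are afterwards repeated with baseline in place of screening.

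On population, section 2.5.3 says: "Biomarker analyses will be performed on biomarker analysis set". That set takes every randomized, dosed subject with a sample, so it covers all hsCRP levels.

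No other section supplies the contrast. The MMRM in section 4.2.2 is fitted "with time, treatment, country, screening hsCRP stratification and time-by-treatment interaction as factors", so hsCRP enters as a main effect and the only interaction is with time. The logistic model in section 4.2.4 also carries hsCRP stratum as a main effect. Results by hsCRP stratum in sections 2.6, 4.2.3 and 4.2.4 are descriptive.

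**The concern.** Two questions share the word predictive. One is whether hsCRP is associated with improvement among treated subjects. The other is whether the benefit of sirukumab over placebo depends on hsCRP. A one-arm regression answers only the first. If subjects with higher hsCRP improve more, or less, whatever they receive, the sirukumab model finds it and the rule is met although the drug effect is the same at every hsCRP level.

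The SAP sees the distinction, since it adds a placebo fit to show specificity. But specificity is a statement about the difference between two slopes, and that difference is not named as something to estimate. What counts as having shown it is left open until the results are in.

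This matters because hsCRP defines the primary population and the randomization strata, so a report that it is a specific predictor would carry weight. Section 5.2.2.1 also uses the baseline hsCRP model as its benchmark: markers with "better performance than the hsCRP model are identified as alternate candidate predictive biomarkers", and that section mentions neither arm nor a placebo comparison.

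**Working it through.** **The plan's own figures.** Section 5.2.1 gives a threshold (0.1) but no power or error rate to reproduce. The SAP's one design figure, 142 subjects with hsCRP >= 3.00 mg/L, does reproduce. 2 x (8 x (1.150 + 1.282)/4)^2 = 47.3, so 48 per arm, and 96/(0.75 x 0.90) = 142.2. It is not in question here.

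**Inputs.**
- About 96 randomized per arm and 25% drop-out (section 1.4): 96 x 0.75 = 72 per arm with Week 12 data.
- Three covariates: BMI, sex, age (section 5.2.1).
- p <= 0.1, taken as two-sided because the criterion concerns variance explained. The SAP does not state the sides.
- Partial correlation r of hsCRP with HDRS17 change: not in the SAP, so a range is assumed.

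**Step 1: hsCRP equally prognostic in both arms, so true specificity is zero.** Simulated trials, 72 per arm:

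| r in both arms | One-arm rule met | Slope difference flagged at 0.1 |
|---|---|---|
| 0.1 | 22% | about 10% |
| 0.2 | 50% | about 10% |
| 0.3 | 81% | about 10% |
| 0.4 | 97% | about 10% |

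A noncentral-t calculation agrees closely. At r = 0.2 the noncentrality is 0.2/sqrt(1 - 0.04) x sqrt(72) = 1.73, giving 53%.

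**Step 2: precision of the missing contrast.** Each arm-wise fit has 72 - 5 = 67 residual degrees of freedom. In SD units, with hsCRP unrelated to the covariates, the slope SE is about sqrt((1 - r^2)/67). The arms are independent, so SE(difference) = sqrt(SE1^2 + SE2^2).
- r = 0 in both arms: sqrt(2/67) = 0.173; x 1.645 = 0.28.
- r = 0.4 in both arms: sqrt(2 x 0.84/67) = 0.158; x 1.645 = 0.26.

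If the design SD of 8 applies, that is +/-2.1 to +/-2.2 HDRS17 points per SD of hsCRP (0.26 x 8 and 0.28 x 8).

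**Step 3: power with no association on placebo.** SE = sqrt((1 + 1 - r^2)/67); power is about Phi(r/SE - 1.645).
- 0.2: SE 0.171, Phi(-0.48) = 32%.
- 0.3: SE 0.169, Phi(0.13) = 55%.
- 0.4: SE 0.166, Phi(0.77) = 78%; simulation gives 77% to 78%.

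**Step 4: which model.** A pooled model with treatment-by-hsCRP but common slopes for BMI, sex and age is not safe. If BMI acts differently by arm (slope difference d) and correlates with hsCRP (c), about c x d leaks into the hsCRP interaction. With c = 0.5 and d = 0.4 the bias is 0.20. Against an SE near 0.17, the chance of rejection is about Phi(0.20/0.17 - 1.645) = 32%. Simulated rejection at nominal 10%, with equal hsCRP slopes of 0.2 and BMI related to outcome on sirukumab only:

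| hsCRP-BMI correlation | BMI slope 0.2 | 0.3 | 0.4 |
|---|---|---|---|
| 0.3 | 12% | 15% | 18% |
| 0.5 | 16% | 23% | 31% |

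The difference of the two arm-wise slopes stays at about 10% throughout. Correlation with BMI does widen its interval by 1/sqrt(1 - c^2): at c = 0.5, 0.28 x 1.15 = 0.32.

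**The case against.** The best defence is that this is biomarker work outside the primary analysis, that objective 12 asks only about correlation, and that both arms' coefficients and significance levels are reported. An SE follows from a coefficient and its p-value, and the arms are independent, so any reader can form the slope difference. That stands. It rules out saying that the plan leaves no way to decide. What is missing is a stated contrast with an interval, and a commitment that the specificity claim rests on it.

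Four stronger readings are tempting and not supported.

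- A reader might infer that specificity will be declared when hsCRP is significant on sirukumab and not on placebo. The SAP does not say so. That pattern would arise in 16%, 25%, 15% and 3% of trials at equal r of 0.1 to 0.4, but this describes one possible reading of the comparison, not the plan.
- A reader might take 22% to 97% as false-positive rates. They are the chances of detecting a true association, which is what objective 12 seeks.
- A reader might extend the point to objectives 7, 10 and 11, which are worded as comparisons between subgroups. Section 2.6 makes the subgroup work openly descriptive, and section 4.2.4 is plain: "Response rate or remission rate at Week 12 will be provided by treatment group for the following subgroups". The stratum below 3.00 mg/L is one of the four, counts in the other three add up to the rest, and mITT3 is the group at or above 3.00 mg/L at screening.
- A reader might read section 5.2.2.1 as naming established predictors. Its label is candidate, and the baseline repeat in 5.2.1 follows the placebo sentence, so its benchmark plausibly has a placebo counterpart.

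**Conclusion.** The point holds, within limits. Section 5.2.1 attaches the label predictive to a one-arm association and sets out to show specificity without planning the estimate that specificity consists of. This follows from the text and needs no assumed figure.

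The figures show scale only. A purely prognostic marker would meet the rule in about 22%, 50% and 81% of trials at r = 0.1, 0.2 and 0.3. They rest on assumed correlations, 72 evaluable subjects per arm and a two-sided threshold.

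The change is worth making because the section names the goal and the better method is nearly free. It bears on how the hsCRP result may be described, and it does not touch the primary test.

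**What to change.** In section 5.2.1, for HDRS17 change and percent change, add the difference between the sirukumab and placebo hsCRP slopes with a 90% CI, which matches the section's 0.1 threshold. Leave covariate slopes free by arm. Either of two routes will do:

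- the difference of the two planned arm-wise slopes, with SE = sqrt(SE1^2 + SE2^2); or
- one pooled model with treatment-by-hsCRP plus treatment-by-BMI, treatment-by-sex and treatment-by-age terms.

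Do not use a pooled model with common covariate slopes. State that any claim of specificity rests on this estimate and its CI, and describe a one-arm p <= 0.1 as an association. Keep the arm-wise fits, logistic models and ROC curves as description.

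The cost is a few sentences in the SAP and a small calculation on data already collected. The drawback is width: about +/-0.26 to +/-0.28 SD per SD, more if hsCRP tracks BMI, with power of about 32%, 55% and 77% for true slope differences of 0.2, 0.3 and 0.4. The SAP should say in advance that an interval covering zero does not exclude specificity.
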